7.8.2 Laboratory data

The analyses of laboratory data will be descriptive in nature and will be based on BI standards. Central laboratory data will be used for all displays described below, unless otherwise specified. Summaries of eGFR and UACR will be included as part of the routine summaries of laboratory variables.

For continuous safety laboratory variables where reference ranges exist, normalised values will be derived (i.e. transformation to both a standard unit and to a standard reference range). Descriptive statistics will be presented over time for absolute values and changes from baseline in each of the laboratory variables where normalised values are possible. All scheduled weeks will be presented as well as last value, minimum value and maximum value on-treatment.

For continuous safety laboratory variables where reference ranges exist, a shift table will be produced summarising the shifts from baseline to the last value on treatment, and displaying categories “Low”, “Normal” and “High” with respect to the relevant reference range. Standardised values (i.e. transformation to a standard unit only) will be used for this purpose.

For categorical safety laboratory variables, a shift table will be produced summarising the shifts from baseline to the last value on treatment, and displaying each relevant category. For any semi-quantitative variables (i.e. those recorded as either “Normal” or with a continuous numerical value otherwise), the shift table will display categories “Normal” and “Abnormal”

only, without further categorisation of the continuous values into different degrees of abnormality.

Potentially clinically significant abnormalities will be identified using BI standard rules. A listing containing these rules (including for each variable whether a low range applies, or a high range applies, or both) will be included. A frequency table will be used to summarise the number and percentage of patients with potentially clinically significant abnormalities, for each variable where a BI standard rule exists. Patients with an abnormal value at baseline will be presented separately on this table.

A separate listing will present potentially clinically significant abnormal lab values; for each functional lab group all patient's laboratory values will be listed, if there exists at least one value with clinically significant abnormality within the group.

The following additional investigations will be made for elevated liver enzymes:

A frequency table will be produced of the following categories. A patient will be included in each relevant category, defined using the maximum post-baseline ALT and AST values observed on-treatment ([Section 6.1.6](#)), regardless of the baseline AST and ALT values:

- ALT or AST ≥ 3 x ULN
- ALT or AST ≥ 5 x ULN
- ALT or AST ≥ 8 x ULN
- ALT or AST ≥ 10 x ULN
- ALT or AST ≥ 20 x ULN
- ALT or AST ≥ 3 x ULN with total bilirubin ≥ 2 x ULN
- ALT or AST ≥ 3 x ULN with INR ≥ 1.5
- ALT or AST ≥ 3 x ULN with either total bilirubin ≥ 2 x ULN or INR ≥ 1.5

In the above categories, each occurrence within a patient of a post-baseline elevation ALT or AST ≥ 3 x ULN will be used as a trigger for the determination of the elevation of total elevation of bilirubin ≥ 2 x ULN or INR ≥ 1.5 , as applicable. The proposed time interval for the follow-up of total bilirubin or INR is 30 days after the occurrence of the post-baseline ALT or AST elevation.

The above frequency table will be repeated using the same categories, but restricted further to patients with a normal baseline value for ALT and AST, defined as both ALT < ULN and AST < ULN.

An additional frequency table will be produced for patients who have an abnormal baseline value for ALT or AST, defined as ALT \geq ULN or AST \geq ULN (or both), and who fall into each of the following categories:

- Both baseline ALT and AST < 2 x ULN and post-baseline ALT or AST > 5 x baseline value
- At least one of baseline ALT or AST ≥ 2 x ULN and < 5 x ULN and post-baseline ALT or AST > 3 x baseline value

- At least one of baseline ALT or AST ≥ 5 x ULN and post-baseline ALT or AST > 2 x baseline value
- Post-baseline ALT or AST > 2 x baseline value with total bilirubin ≥ 2 x ULN or increase in INR > 0.2 .

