### 5.2.3 Safety laboratory parameters

Safety laboratory parameters to be assessed are listed in [Table 5.2.3: 1](#). For the sampling time points please see the [Flow Chart](#). Patients do not have to be fasted for the blood sampling for the safety laboratory.

Analyses will be performed by a central laboratory; the respective reference ranges will be provided in the ISF. Instructions regarding sample collection, sample handling/ processing and sample shipping are provided in the laboratory manual.

The central laboratory will send reports to the Investigator. It is the responsibility of the Investigator to evaluate the laboratory reports. Clinically relevant abnormal findings as judged by the Investigator will be reported as AEs (please refer to [Section 5.2.6](#)).

In case the criteria for hepatic injury are fulfilled, a number of additional measures will be performed (please see [Section 5.2.6.1](#)) and the DILI Checklist provided in the ISF. The amount of blood taken from the patient concerned will be increased due to this additional sampling.

The central laboratory will transfer the laboratory data to the Sponsor periodically.

Table 5.2.3:1 Safety laboratory tests

Category	Test name
Haematology	Haematocrit Hemoglobin MCV (Mean Corpuscular Volume) MCH (Mean Corpuscular Haemoglobin) MCHC (Mean Cellular Haemoglobin Concentration) Red Blood Cell Distribution Width (RDW) Red Blood Cells (RBC) Count/ Erythrocytes WBC Count/ Leukocytes Platelet Count / Thrombocytes Differential Automatic (relative and absolute count): Neutrophils, Eosinophils, Basophils, Monocytes, Lymphocytes
Clinical chemistry	Albumin Alkaline phosphatase Amylase ALT (alanine aminotransaminase, SGPT) AST (aspartate aminotransaminase, SGOT) Bicarbonate Bilirubin total, fractionated if increased Calcium
Clinical chemistry	Chloride Creatinine Creatine kinase (CK) CK-MB, troponin (reflex tests if CK is elevated) Ferritin $\gamma$ -GT (gamma-glutamyl transferase) Glucose (plasma, not fasted) HbA1c/ Insulin/ C-Peptide** Lactate dehydrogenase (LDH) Lipase Magnesium Phosphate Serum Free Fatty Acids Potassium Protein total Sodium Urea (blood urea nitrogen, BUN) Uric acid Thyroid stimulating hormone (TSH)* Calcitonin* eGFR (CKD-EPI formula)
Coagulation	Activated Partial Thromboplastin Time (aPTT) Prothrombin Time (INR) Fibrinogen
Lipids	Cholesterol (total) HDL cholesterol LDL cholesterol (including VLDL) Triglycerides

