Table 5.2.3:1 Safety laboratory tests (cont.)

Infectious serology	Hepatitis B surface antigen (HBsAg)* Hepatitis B surface antibodies (anti-HBs)* Total hepatitis B core antibodies (anti-HBs)* Hepatitis C antibodies (anti-HCV)*
Urinalysis	Semi quantitative Nitrite Protein Ketone Urine pH Leukocyte esterase (for WBC) Blood (erythrocytes)  Quantitative*** Albumin Creatinine  Urine drug screen* Cannabis Cocaine Benzodiazepine Amphetamines Barbiturates Methadone Opiates

\* Measured only at Visit 1.

\*\* Measured only at Visit 1, Visit 2, Visit 27 and at the EOT/ED visit.

\*\*\* Albumin/creatinine ratio in spot urine will be calculated at the central laboratory.

SARS-CoV-2 RT PCR test will be performed at Visit 1.

ADAs, NABs, level of BI 456906, IgE, histamine, serum tryptase, and complement components will be analyzed in the event of systemic hypersensitivity.

If the assessment of safety laboratory tests in the central laboratory is not possible due to emergency, pandemic or other unforeseen circumstances, the assessment will be performed in the local laboratories.

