### Pregnancy tests:

All women of childbearing potential will undergo serum pregnancy test at the screening visit (Visit 1). The test will be done in the central laboratory. Patients with a positive result of the serum pregnancy test will be excluded from the trial. Urine pregnancy tests will be done monthly starting from Visit 2. They will be done locally. If the urine pregnancy test is positive, a serum pregnancy test will be done in the central laboratory to confirm pregnancy. If the serum pregnancy test is positive, trial medication will be discontinued, and patient will be discontinued from the trial. If the serum pregnancy test is negative, the patient may continue in the trial. If the urine pregnancy test is positive at the randomization visit (Visit 2), the patient must not be randomised into the trial unless the serum pregnancy test is negative.

In the event of disruptive circumstances (e.g., pandemic, war) the investigational plan as per this clinical trial protocol may not be feasible at a site. In this case, Sponsor, and Investigator, with the informed consent of the patient, may agree on alternative, back-up methodology which may include but will not be limited to allowing local labs for safety assessments, providing options to either consider paper diaries or paper PROs for patients, and other measures that may be required to ensure trial continuity while maintaining patient safety and data integrity of primary endpoint.

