reader instead of the primary reader. The meaning of “adequate” is given in [Section 5.1](#).

- The first screening central pathology reading (i.e. as used to assess eligibility) will be used for baseline in all cases where a re-reading of the screening biopsy was subsequently done, unless otherwise specified for any analysis. For sites in China (only), the first screening central pathology reading is a digital reading and this will be used.

MRI-PDF and [REDACTED] procedures are only scheduled to be performed at screening, and not also at the randomisation visit. Therefore, the baseline value is the screening value in these cases.

Visit windows

All summaries and analysis which are presented by week will use a visit window to classify the data record. This approach allows appropriate classification of visits which may have occurred significantly earlier or later than the protocol assessment schedule, as well as the use of data captured at visits which have no fixed timing (notably the EOT visit). Relative day will be defined for this purpose as $(date\ of\ assessment - date\ of\ first\ administration\ of\ study\ medication) + 1$.

Nominal database visit labels will not be used in any summary or analysis by time point, unless otherwise stated.

Prior to applying the rules for handling multiple values in visit windows specified below, it will first be determined whether the data record is on-treatment, as defined in [Section 6.1.6](#), for all summaries or analysis which require this approach.

Unscheduled and repeat assessments (where relevant/available) are eligible for inclusion in visit windows.

For all variables except 12-lead ECG, if a patient has more than one non-missing value within the same visit window, the value closest to the target day will be selected. If two non-missing values are the same distance from the target day, the earlier of the two values will be selected.

For 12-lead ECG (only), scheduled visits take precedence over unscheduled visits. Once this rule has been applied, the measurement closest to the target day will be used. If there are two observations which have the same difference in days to the planned day (but are not on the same day), the later of the two values will be selected.

Derivation of last, minimum and maximum values where relevant in safety analyses will consider all available values, regardless of whether they were selected in the visit window.

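### SAP 7.8.2 limits the liver laboratory tables to central results although the protocol provides for local testing, so elevations measured only locally go uncounted

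*SAP*

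**What the plan says.** The protocol's default is central testing: "Analyses will be performed by a central laboratory" (Protocol 5.2.3). The end of the same section adds a fallback. If the central assessment "is not possible due to emergency, pandemic or other unforeseen circumstances, the assessment will be performed in the local laboratories". Under this rule the local result replaces the central one; it is not a duplicate. Protocol 6.1, in the closing paragraph on disruptive circumstances, is softer: the sponsor and investigator may agree on back-up methods, which may include "allowing local labs for safety assessments".

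SAP 7.8.2 then fixes the data source for everything that follows it: "Central laboratory data will be used for all displays described below, unless otherwise specified". The displays that follow are the descriptive statistics, the shift tables, the potentially clinically significant abnormality table and listing, and three ALT/AST frequency tables (all patients, normal baseline, abnormal baseline). In the all-patient table, and in its repeat for patients with normal baseline, patients are placed in categories "defined using the maximum post-baseline ALT and AST values observed on-treatment". Each rise to 3 x ULN or more is then paired with a later bilirubin or INR: "The proposed time interval for the follow-up of total bilirubin or INR is 30 days".

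Neither document says how local results are recorded, standardised or displayed.

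**The concern.** The protocol foresees on-treatment safety results that exist only as local values, and the SAP has a rule that leaves such values out of every laboratory display. The liver tables are the most exposed. They rest on each patient's single highest value and on the pairing of two results within a short interval, so one missing result can move a patient out of a category.

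Hepatic injury is the only AESI that the protocol pre-specifies, and the protocol defines it by laboratory alterations. The tables in SAP 7.8.2 are the threshold-based check on it that does not depend on what an investigator chose to record. If a combined row (ALT or AST at 3 x ULN or more with raised bilirubin or INR) shows zero, a reader could not tell a true zero from a case that was measured locally and left out.

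**Working it through.** No power, alpha or event-rate figure underlies this point, so the check is mainly a comparison of texts.

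**Step 1: is there an exception?** The visible text of SAP 7.8.2 gives none. The nearest candidate is in SAP 6.7: "Derivation of last, minimum and maximum values where relevant in safety analyses will consider all available values". The sentence goes on to say that this applies whether or not the value was selected for a visit window. It settles which time points count, not which laboratory. SAP 7.9, on COVID-19 impact, covers missed visits, discontinuations and SARS-CoV-2 adverse events, but not local laboratory results.

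**Step 2: what happens to a local-only result?** Take a treated patient with central on-treatment results C and local-only on-treatment results L.

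| Situation | Under SAP 7.8.2 as written |
|---|---|
| ALT/AST peak is in L, and all of C is below the threshold | Patient is not in that category |
| ALT/AST rise to 3 x ULN or more is in C, but the raised bilirubin or INR within 30 days is in L only | Single-enzyme row counts the patient; combined row does not |
| Rise and paired result are both in L | Neither row counts the patient |
| Peak also measured centrally | No effect |

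**Step 3: direction.** For a threshold k, a patient counts if the maximum reaches k. Since max(C) ≤ max(C and L together), the count from C alone cannot exceed the count from C and L together. The same holds for the combined rows: adding results can create qualifying pairs but cannot remove any. Each count can therefore only be too low. The direction of the error in a difference between arms is not determined, because that depends on where the local results fell.

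**Step 4: size.** The documents give no rate of local testing, so the number of affected patients cannot be computed. What can be stated is the step per patient:

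- Planned arm size 60: 1/60 = 1.7 percentage points.
- By actual treatment, using the most unequal split considered in Protocol 7.5 (60/90/50/40): from 1/90 = 1.1 to 1/40 = 2.5 points.

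These figures are units of change, not estimates of how far any row is wrong.

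**Step 5: where can local values be used?**

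| Display in SAP 7.8.2 | Scale | Can a local value enter the count? |
|---|---|---|
| ALT/AST and bilirubin rows, all patients and normal baseline | Multiples of ULN | Yes, against the local laboratory's ULN |
| INR in those tables | Absolute, 1.5 | Yes, directly; no ULN is involved |
| Abnormal-baseline table | Multiples of baseline; INR increase above 0.2 | Not cleanly; a local value over a central baseline is a cross-assay ratio |
| Clinically significant abnormality displays | Sponsor's standard rules, not shown | Cannot be judged from the documents |
| By-visit, normalised and shift summaries | Common unit or reference range | No; central only is reasonable |

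**The case against.** The case for leaving the rule alone has real substance.

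- **Other tables still show these cases.** A reader might infer that locally measured liver injury disappears from the report. The documents do not support that. Hepatic injury is reported as an AESI, with no stated requirement that the result be central. SAP 7.8.1 tabulates investigator-recorded AESIs and a set of liver-related MedDRA queries, and Protocol 5.2.3 has clinically relevant abnormal findings reported as adverse events. The gap is confined to the laboratory displays. It still matters there, because the adverse event tables depend on investigator recording and the laboratory tables do not.
- **Repeat tests are not stated to be local.** Protocol 10.1 asks for repeats within 48 to 72 hours, and it is tempting to assume these are local. The protocol does not name the laboratory, central testing is the default, and central repeats do count towards the maximum. The point rests on the fallback in Protocol 5.2.3, not on Section 10.1.
- **Protocol 6.1 only permits.** It allows local laboratories by agreement and does not by itself make local results the trial's data.
- **No conclusion hangs on one case.** Safety is descriptive with no hypothesis testing, and no decision rule is tied to these rows. Nothing in the documents supports a claim about how many combined cases to expect, or that one omission would overturn a conclusion.
- **A single assay has value.** Central-only data keep one method and one reference range, which the normalised and shift summaries need.

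All of this stands and limits the scope. It does not answer the narrower point: the SAP states a rule that, where the Protocol 5.2.3 fallback supplied the only qualifying result, lowers the liver counts.

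**Conclusion.** The point holds in limited form. As written, SAP 7.8.2 leaves out of the laboratory-based liver tables any on-treatment ALT/AST peak, and any bilirubin or INR within 30 days of a rise, that was measured only locally. The error in those counts runs one way, towards too few. Its size is unknown and may be nil; each affected patient is worth 1.7 points in an arm of 60.

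This rests on three assumptions: that local testing was used for at least some patients on treatment, that the decisive value was not also measured centrally, and that no exception stands outside the visible SAP text. It is a cheap improvement to a safety display. It does not touch the efficacy analysis, and it does not show that hepatic cases go unreported.

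**What to change.** Amend SAP 7.8.2 as follows.

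1. **ALT/AST tables on multiples of ULN (all patients, and normal baseline).** Count local on-treatment ALT, AST and bilirubin as multiples of the local laboratory's own ULN, and local INR against the absolute 1.5 cut-off. Do this in the main table or in a repeat of it, and flag every patient classified by a local value.
2. **Abnormal-baseline table and clinically significant abnormality displays.** List the local values and do not mix them into the counts.
3. **By-visit, normalised and shift summaries.** Keep central only.

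The cost is SAP wording, mixed assays in the threshold rows (which the flag makes visible), and entry of local values and reference ranges if they were not already captured. The documents do not show whether they were. With the revised SAP dated 19 January 2024 and due to be final before database lock, this could mean some retrospective collection. If that is not feasible for every patient, a repeat table restricted to the local values in hand, labelled as such, would still tell the reader whether the central-only counts are complete as far as is known.

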7.8.3 Vital signs

Descriptive statistics will be presented over time for absolute values and changes from baseline in each of the vital signs variables, and will include display of pre- and post-dose at each scheduled week.

7.8.4 ECG

Abnormal findings will be reported as baseline conditions (at screening) or as AEs (during the trial) if judged clinically relevant by the investigator.

The ECG recordings will be centrally evaluated and rated as normal, abnormal, or not evaluable.

All derivations relating to 12-lead ECG variables are given in [Section 5.4.1](#).

Occurrences of values above thresholds will be flagged in the listings. For QTcB and RR, only listings will be provided.

Quantitative variables

Descriptive statistics will be presented over time for absolute values and absolute changes from baseline in the following quantitative ECG variables: QTcF, HR, QT, QRS, PR.

Graphical summaries over time will also be included.

Categorical variables

Frequency tables will be provided for the categorical variables described below, which are determined from the specified quantitative ECG variables:

- New onset (meaning that this or a higher category was not present any time at baseline) of maximum QTcF interval > 450 to 480 msec, > 480 to 500 msec, or > 500 msec on treatment.
- New onset (not present any time at baseline) of uncorrected QT interval > 500 msec at any time on treatment
- Maximum change from baseline of QTcF ≤ 30 msec, > 30 to ≤ 60 msec, or > 60 msec on treatment.
- Maximum change from baseline of QT ≤ 60 msec, or > 60 msec on treatment.

For assignment of a particular patient to one of the above categories, all available time points on-treatment will be considered.

The occurrence of any of the following will be considered as “notable findings” and summarised using frequency tables:

- New onset (not present any time at baseline) of uncorrected QT interval > 500 msec at any time on treatment
- New onset of QTcF interval > 500 msec at any time on treatment
- Change from baseline of QTcF > 60 msec at any time on treatment
- Percentage change from baseline of HR $\geq 25\%$, when corresponding on-treatment value of HR is > 100 beats/min, or percentage change from baseline of HR $\leq -25\%$, when corresponding on-treatment value of HR is < 50 beats/min, at any time on-treatment
- Percentage change from baseline of PR $\geq 25\%$, when corresponding on-treatment value of PR interval is > 200 msec, at any time on treatment
- Percentage change from baseline of QRS $\geq 10\%$, when corresponding on-treatment value of QRS duration is > 110 msec, at any time on treatment.

Frequency tables will also include morphological findings (determined and categorized based on SDTM terminology) that might be attributable to treatment. In particular, new onsets of findings not present at baseline will be explored. A morphological finding observed on treatment that was not reported at baseline will be categorized as a ‘new onset’ of this finding.

For all patients with any notable finding in ECG intervals, a separate listing will be created as end-of-text display, and the corresponding time profiles will be shown.

A shift table will be produced for QTcF, summarising the shifts from baseline to the maximum value on treatment, and displaying categories “ ≤ 450 msec”, “> 450 to 480 msec”, “> 480 to 500 msec and “> 500 msec”.

A scatter plot of QTcF at baseline and the maximum change from baseline (based on all on-treatment values as defined in [Section 6.1.6](#), and the maximum evaluated regardless of whether these were selected based on visit windows described in [Section 6.7](#)) will be produced. The plot will include diagonal reference lines for absolute QTcF equal to 450 msec, 480 msec and 500 msec, as well as horizontal reference lines for QTcF maximum changes from baseline equal to 30 msec and 60 msec.

Appropriateness of heart rate correction methods of QT interval

To evaluate the appropriateness of the heart rate correction methods, the slope of the relationship of the (untransformed) QTcF interval versus RR interval will be estimated for off-drug values and for each Survodutide maintenance dose group separately by applying a random coefficient (random slope and intercept) model. Off-drug values for this purpose are defined as only values (either baseline or on-treatment values as defined in [Section 6.1.6](#)) from patients randomised to placebo, since patients randomised to Survodutide dose groups are expected to have a single ECG at baseline only, and therefore cannot contribute a slope for estimation of an off-drug random effect for this. For the Survodutide maintenance dose group analyses, only on-treatment values will be used, and these will be included regardless of Survodutide dose (i.e. data from the dose escalation period will be included). The model will be fitted using the QTcF and RR pairs at each time point, using all values within the visit windows defined in [Section 6.7](#). A scatter plot of QTcF versus RR will be produced, and will

include the overall regression line obtained from the model. The population estimate of the slope together with its two-sided 95% confidence interval will be displayed in a footnote to the plot.

The slope of the relationship of the log-transformed (uncorrected) QT interval versus log-transformed RR interval will be estimated for off-drug values and for each Survodutide maintenance dose group separately by applying a random coefficient (random slope and intercept) model similar to above, with off-drug values and data selection defined in the same way. A scatter plot of log(QT) versus log(RR) will be produced, and will include the overall regression line obtained from the model. The population estimate of the slope together with its two-sided 95% confidence interval will be displayed in a footnote to the plot.

